6 SUBJECT SELECTION

6.1 Study Population

Subjects who are planned to undergo minimally invasive lung resection and meet the inclusion and exclusion criteria will be eligible for participation in this study. Of note, subjects with non-English proficiency will be eligible for participation in this study: Spanish, Cantonese, Mandarin, Russian. These subjects will be provided written Consent, Experimental Subject's Bill of Rights, and HIPAA Authorization in their preferred language with use of a Qualified Interpreter.

6.2 Inclusion Criteria

1. Robot or video-assisted lung resection for all indications
Robotic or video-assisted techniques both use three to four incisions that are <15mm and there are no expected differences between the techniques. The indication for surgery is not expected to influence the primary outcome.
2. Surgeons: [name] MD, [name] MD, or [name] MD
3. Written informed consent obtained from subject or subject's legal representative and ability for subject to comply with the requirements of the study.

6.3 Exclusion Criteria

1. Additional thoracic procedures performed beyond lung resection and mediastinal lymphadenectomy (such as chest wall resection, rib resection, muscle flap, etc) and/or extra-thoracic procedures (such as abdominal surgery, neck surgery, etc).
Additional procedures will alter postoperative course and postoperative pain.
2. Reported hypersensitivity to amide local analgesia (such as lidocaine, bupivacaine, ropivacaine).
3. Reported Cardiac Conduction Abnormalities (Wolf-Parkinson-White, second degree Mobitz II or third degree atrioventricular heart block).
Amide local analgesia can cause heart block and/or cardiac arrest.
4. Hepatic Dysfunction defined as cirrhosis complicated by ascites, esophageal varices, or hepatic encephalopathy determined by preoperative history and physical.
Amide local analgesia is metabolized by the liver.

5. Renal Dysfunction requiring hemodialysis or peritoneal dialysis determined by preoperative history and physical.
Amide local analgesia excreted by the kidneys.
6. Preoperative Neuropathic Pain requiring tricyclic antidepressants or calcium channel alpha 2-delta ligands (gabapentin, pregabalin).
To compare subjects without preoperative neuropathic pain.
7. Preoperative Daily Opioid Usage.
To compare subjects without preoperative pain requiring opioids.
8. Pregnant or breastfeeding during participation in the study.
Subjects not eligible for surgery or the study.
9. <18 years of age.
10. Presence of a condition or abnormality that in the opinion of the investigator would compromise the safety of the patient or the quality of the data.

7 CONCURRENT MEDICATIONS

Intraoperative analgesia provided by the anesthesia team will not be altered and will be performed per standard care. All subjects will be started on the same postoperative pain medications in the hospital and when discharged as outlined in Section 7.1.

7.1 Allowed Medications and Treatments

Standardized Hospital Pain Medication Regimen:

Medication will not be given if there is known allergy. Goal pain management is to allow the subject to ambulate and perform incentive spirometry per standard of care. Escalation of opioid dosing if needed will be at the discretion of the inpatient surgery team.

- PO Tylenol 1000mg every 6 hours
- PO Gabapentin 300mg twice a day
- IV Ketorolac 15mg every 6 hours for 24 hours, then PO Diclofenac 50mg BID (if <75 years old and normal renal function)
- PO Oxycodone 5-10mg every 4 hours as needed for moderate pain
- IV Hydromorphone 0.2-0.4mg every 2 hours as needed for severe pain

Standardized Discharge Pain Medication Regimen:

All subjects to be discharged on the following pain regimen outlined below. Medication will not be given if there is known allergy.

- PO Acetaminophen 1000mg every 6 hours for 2 weeks
- PO Gabapentin 300mg twice a day for 2 weeks
- PO Diclofenac 50mg BID for 2 weeks
- PO Oxycodone as needed for pain – 20 Pills in Total

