8 STUDY TREATMENTS

8.1 Method of Assigning Subjects to Treatment Groups

80 eligible subjects will be randomly assigned to intraoperative intercostal nerve blocks and wound infiltration by Standard Bupivacaine or Liposomal Bupivacaine in a 1:1 ratio with varying block size (4-8) using Stata 15.1 (College Station, TX) ralloc.ado package. When the subject arrives in the operating room, the surgeon/study doctor will contact the pharmacy who will determine treatment assignment and prepare the medication as outlined in Sections 8.3-8.4.

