8.6 Measures of Treatment Compliance

Subject compliance is not an issue with this study as the treatment is given in a single episode by the investigators at the conclusion of surgery. A standardized approach will be

used by all investigators as outlined in Section 8.4.3. To ensure that each subject receives the same postoperative pain management, a standardized electronic orderset will be utilized.

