15.6 Sample Size and Randomization

80 Subjects will be randomized to 1:1 to Liposomal Bupivacaine or Standard Bupivacaine by varying block size (4-8). 80 subjects will provide 80% power to detect a statistically significant effect with 2-sided alpha error set at 0.05 if the measured effect is 19% absolute reduction in cumulative daily in-hospital use of opioids.

The mean daily in-hospital usage of opioids is 35mg morphine equivalents with standard deviation of 12mg. This was estimated by review of previously published studies and corroboration with UCSF clinical practice patterns [12]. A 19% absolute reduction in cumulative daily in-hospital use of opioids corresponds to 1 fewer oxycodone dose per day, which was considered the minimum clinically significant effect.

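### Scheduled in-hospital NSAID cover depends on age and renal function, but the primary opioid comparison does not adjust for NSAID eligibility unless randomization is judged ineffective: a loss of precision, not a bias

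*Combined protocol and SAP*

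**What the plan says.** Section 7.1 lists the standardized hospital regimen. Acetaminophen and gabapentin are scheduled without an age or renal condition, and the opioids are given as needed. The NSAID line carries a condition: "IV Ketorolac 15mg every 6 hours for 24 hours, then PO Diclofenac 50mg BID (if <75 years old and normal renal function". The same section withholds any drug to which there is a known allergy.

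Section 6.3 sets a lower age limit only. Its renal exclusion is "Renal Dysfunction requiring hemodialysis or peritoneal dialysis determined by preoperative history and physical", so lesser renal impairment is admitted.

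Section 7 says all subjects start on the same drugs as set out in 7.1. Section 8.6 goes further: "To ensure that each subject receives the same postoperative pain management, a standardized electronic orderset will be utilized".

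Section 8.1 assigns subjects "in a 1:1 ratio with varying block size (4-8") and names no stratification factor. Section 15.3 compares the arms with Student's t-test, with a transformation or the Mann-Whitney test if normality fails. If randomization is not effective, it turns to linear regression on age, sex, race, comorbidity, diagnosis and procedure. It gives no criterion for that judgement. Neither renal function nor NSAID eligibility appears in that list or among the baseline variables of section 15.2.

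**The concern.** Opioids are the as-needed layer on top of the scheduled non-opioids. A rule that removes one scheduled class from a group identifiable by baseline characteristics can therefore bear directly on the endpoint. The exclusions for daily opioid use, neuropathic pain and additional procedures show that the plan wants subjects comparable in pain and opioid need, yet this source of variation is written into the regimen itself.

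If the two groups do differ in opioid use, the unadjusted t-test leaves that between-group variance in its error term. The trial then detects a given treatment difference with less power than the same 80 subjects could provide.

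**Working it through.** **Inputs from section 15.6.** "The mean daily in-hospital usage of opioids is 35mg morphine equivalents with standard deviation of 12mg"; a "19% absolute reduction in cumulative daily in-hospital use of opioids"; and "80 subjects will provide 80% power to detect a statistically significant effect with 2-sided alpha error set at 0.05". The target difference is 0.19 × 35 = 6.65 mg/day, with 40 subjects per arm. Everything below is on this per-day scale.

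**The plan's own figure.** Normal approximation: n per arm = 2 × (1.960 + 0.842)² × 12² / 6.65² = 51.1, so 52 per arm and N = 104. At 40 per arm the standard error is 12 × √(2/40) = 2.68 mg, and power = Φ(6.65/2.68 − 1.96) = 69.8%. With the noncentral t the results are 53 per arm (N = 106) and 68.7%. The stated 80% is thus not reproduced from the stated inputs. That is a separate matter, but it makes about 70% the starting point here.

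**Assumptions, not in the documents.** Let p be the share of subjects not eligible for the NSAID, 10% to 40%. Let g be the size of their net difference in opioid use, 5 to 10 mg/day. The sign of g does not matter to the variance. The age and renal condition is read as covering the whole NSAID line.

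**Gain from adjustment, taking 12 mg as the total SD.** The flag contributes variance p(1 − p)g², so the residual SD is √(144 − p(1 − p)g²).

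| p | g (mg/day) | p(1 − p)g² | Residual SD | Power, 40 per arm | N for 80% |
|---|---|---|---|---|---|
| any | 0 | 0 | 12.00 | 69.8% | 104 |
| 10% | 5 | 2.25 | 11.91 | 70.5% | 102 |
| 20% | 5 | 4.00 | 11.83 | 71.0% | 100 |
| 30% | 7.5 | 11.81 | 11.50 | 73.5% | 94 |
| 40% | 10 | 24.00 | 10.95 | 77.5% | 86 |

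The standard error falls from 2.68 to between 11.91 × √(2/40) = 2.66 and 10.95 × √(2/40) = 2.45 mg.

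**If 12 mg instead describes uniformly treated subjects.** The unadjusted SD becomes √(144 + p(1 − p)g²) = 12.09 to 12.96, and unadjusted power is 69.1% to 63.1%. Adjustment returns the residual SD to 12 and power to about 69.8%.

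**Chance imbalance is the same quantity.** The between-arm difference in the ineligible share has SD √(2p(1 − p)/40), or 0.067 to 0.110. Multiplied by g, it moves the treatment difference with an SD of 0.34 to 1.10 mg. As a share of the squared standard error that is p(1 − p)g²/144, or 1.6% to 16.7%: exactly the variance share attributed to the flag above. It is already inside the 2.68 mg and must not be added as a second harm.

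**Validity.** Simulation with permuted blocks of 4, 6 and 8 (four settings, p 20% to 40%, g 7.5 to 15 mg/day, 6,000 trials each) gave a mean imbalance of about zero and type I error of 5.0% to 5.5% for the unadjusted t-test. In the three settings with g no larger than 10, simulated power rose from 68–69% unadjusted to 71–76% adjusted.

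**The case against.** **The size is assumed.** This stands. The documents give neither p nor g. NSAID-ineligible subjects also differ in age and renal function, so their net opioid use could be higher, lower or about the same. The 10 mg/day end exceeds the trial's whole target effect.

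**The plan already adjusts for age and comorbidity.** This stands in part. Age is half of the NSAID rule, and comorbidity may capture some renal disease. But a linear age term is not a cut at 75, renal function is not named, and the regression runs only after an undefined judgement that randomization failed.

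**Unstratified blocks are legitimate at 80 subjects.** This stands. A prespecified covariate should recover most of the available precision, and nothing in the documents ranks this factor above surgeon or procedure for stratification.

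**One conditional order set applied alike to both arms is a standardized regimen.** This largely stands. Section 7 imports the conditions of 7.1 by reference; only the wording of 8.6 is too broad. A reader might infer that the randomization assumes identical background analgesia, but neither 8.1 nor 15.6 says so. Nor is the NSAID rule the only source of variation, since drugs are also withheld for known allergy.

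**Renal status may not be settled before assignment.** This stands. Normal renal function is undefined, section 9.2 lists only a pregnancy test, and assignment takes place once the subject is in the operating room. The documents do not show that the flag is already available at that point.

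**Conclusion.** The point holds as a modest, inexpensive gain in precision. By rule the trial enrols two groups with different scheduled non-opioid cover, and the primary analysis uses that information only contingently and in part. With 10% to 40% ineligible and a net difference of 5 to 10 mg/day, adjusting raises power for 6.65 mg/day from about 70% to between 70.5% and 77.5%. If the net difference is near zero, there is essentially no gain. These figures credit nothing to the contingent regression, because it may never be run.

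A reader might infer that unstratified randomization biases the treatment comparison or invalidates the test. The documents do not support that: assignment is random, the NSAID rule is the same in both arms, and type I error stays near 5%. Nor do they support treating stratified lists as necessary.

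**What to change.** 1. Record baseline NSAID eligibility under the 7.1 rule (yes/no) before assignment. Base it on preoperative age and renal status, never on postoperative NSAID receipt, which is observed after randomization.
2. In 15.3 and the SAP still to be written, prespecify this flag as a covariate in the primary comparison whether or not imbalance is seen. State how the non-normal fallback will carry it, for example a linear model on the transformed scale or a van Elteren test stratified by the flag.
3. State how normal renal function is determined for the flag.
4. Reconcile the common-regimen wording in sections 7 and 8.6 with the conditions in 7.1 (age, renal function, known allergy). This takes no view on the clinical rule.

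The cost is one CRF field, one degree of freedom (77 residual instead of 78) and the work of defining the renal criterion. Separate randomization lists by the flag are optional; they would mean a second pharmacy list and up to two incomplete blocks at the end.

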9.2 Clinical Laboratory Measurements

9.2.1 Pregnancy Test

A urine pregnancy test will be obtained from female subjects who are of childbearing age on the day of their surgery.

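### The age and renal limit on in-hospital diclofenac in Section 7.1 is missing from the discharge list, which gives the same drug and dose to all subjects for two weeks

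*Combined protocol and SAP*

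**What the plan says.** Section 7.1 sets out two standardized pain regimens, one for the hospital stay and one for discharge.

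- **In hospital**, the NSAID line reads "IV Ketorolac 15mg every 6 hours for 24 hours, then PO Diclofenac 50mg BID (if <75 years old and normal renal function", where the parenthesis closes.
- **At discharge**, the list opens with "All subjects to be discharged on the following pain regimen outlined below". It repeats that a drug is withheld for known allergy, then includes "PO Diclofenac 50mg BID for 2 weeks" with no age or renal condition.

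The introduction to Section 7 adds: "All subjects will be started on the same postoperative pain medications in the hospital and when discharged as outlined in Section 7.1". The synopsis likewise describes a standardized discharge regimen for all subjects, without an age or renal condition.

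On who can enter the trial, Section 6.3 excludes subjects under 18 and sets no upper age. Its only specific renal exclusion is "Renal Dysfunction requiring hemodialysis or peritoneal dialysis". Exclusion 10 lets the investigator keep out subjects whose condition would compromise safety or data quality.

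On delivery, Section 8.6 says: "To ensure that each subject receives the same postoperative pain management, a standardized electronic orderset will be utilized".

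**The concern.** The protocol restricts a drug by age and renal function in one list, then gives the same drug at the same dose to everyone in the next list. The second course is a fixed two weeks and is taken at home.

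The protocol does not say why the in-hospital line is restricted. An age and renal cut-off on an NSAID is most plausibly a safety limit. On that reading, the discharge line gives the drug to exactly the subjects from whom it was withheld in hospital.

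What is at stake is avoidable exposure of older or renally impaired subjects to a background drug. The trial's main comparison is not at stake. The primary endpoint is in-hospital opioid use, so a discharge prescription cannot affect it, and the same discharge list applies to both arms.

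**Working it through.** The protocol states no figure to reproduce. The check is a comparison of text, followed by one line of dose arithmetic.

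**1. The two lines side by side (Section 7.1)**

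| | In hospital | At discharge |
|---|---|---|
| Drug, dose, frequency | Diclofenac 50 mg by mouth twice daily, after 24 hours of ketorolac | Diclofenac 50 mg by mouth twice daily |
| Duration | Not stated | 2 weeks |
| Age condition | Under 75 | None |
| Renal condition | Normal renal function | None |
| Allergy exception | Yes | Yes |

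The in-hospital parenthesis could govern the whole ketorolac-then-diclofenac line or diclofenac alone. Diclofenac is restricted under either reading. The allergy exception was repeated for discharge; the age and renal condition was not.

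**2. Does another section carry the limit over?** No. The introduction to Section 7 refers back to 7.1 without adding a condition. The synopsis adds none and lists no prohibited medications.

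**3. Could an affected subject be enrolled?** Yes. Section 6.3 has a lower age bound only, and its named renal exclusion covers dialysis only. Exclusion 10 may remove some subjects at entry, but it is a judgment about enrolment and not a rule on discharge drugs. The in-hospital condition itself presupposes that such subjects can be in the trial; otherwise it would have no purpose.

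**4. Exposure per affected subject, from the protocol dose**

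- Doses after discharge: 14 days × 2 per day = 28
- Daily dose: 2 × 50 mg = 100 mg
- Total after discharge: 28 × 50 mg = 1,400 mg
- Diclofenac in hospital under the 7.1 limit: 0 mg

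These are prescribed amounts. Actual intake depends on adherence.

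**5. Number affected.** The documents give no age or renal-function distribution for the 80 planned subjects, so this cannot be calculated.

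**The case against.** The strongest reply is that the protocol does not force the bad outcome. Section 17.5, item 1, lets the investigator depart from the protocol to protect a subject's safety, so a clinician may withhold diclofenac at discharge. That is true, and the text therefore does not make the prescription inevitable. But this is a general override. It does not supply the missing condition, and it leaves the clinician departing from the written regimen to do what the protocol already requires in hospital. Section 8.6 also relies on a standardized orderset, so an unrestricted line could be built into orders.

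A second reply is that universal wording is not meant literally here. The synopsis says that all subjects receive the standardized hospital regimen, yet that regimen is conditional in 7.1. This weakens the inference that the drafters intended an unconditional discharge order. They may well have meant the limit to carry over. In that case the text is incomplete, and the same correction applies.

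Third, the side arguments about testing and monitoring are weak, and the conclusion does not rest on them. The only laboratory test the protocol schedules is the urine pregnancy test (Section 9.2.1 and Appendix 1). However, the in-hospital rule already needs renal function to be known, so it should be known by discharge if that rule is followed. Section 10.1, item 8, also provides for routine preoperative studies as clinically indicated. Its list names no renal test but is not closed. The inpatient monitoring described in Section 5.3 is not NSAID-specific, and adverse events continue to be collected after discharge.

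Finally, 1,400 mg is an exposure and not a measured harm. That stands: no risk is quantified here.

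**Conclusion.** The concern holds: Section 7.1 is wrong as written. Followed literally, it prescribes 28 doses (1,400 mg) of diclofenac at discharge to eligible subjects whom the same section bars from the drug in hospital.

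Confidence in the textual mismatch is high. Its importance as a safety matter rests on one assumption, that the in-hospital limit exists for safety, which the protocol does not state. The number of subjects affected is unknown; known allergy and exclusion 10 would reduce it.

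The point should be corrected, but it does not threaten the trial's inference. The primary endpoint and the sample size are unaffected, and no between-arm bias is claimed.

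**What to change.** Add the condition from the in-hospital line (under 75 years old and normal renal function) to the discharge diclofenac line in Section 7.1. Then check that the standardized electronic orderset in Section 8.6, and any electronic orders used at discharge, carry the same condition. If the two lists are meant to differ, give the reason in Section 7.1.

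The cost is one parenthetical on one line and a check of the orders. Design, endpoints and sample size do not change.

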8 STUDY TREATMENTS

8.1 Method of Assigning Subjects to Treatment Groups

80 eligible subjects will be randomly assigned to intraoperative intercostal nerve blocks and wound infiltration by Standard Bupivacaine or Liposomal Bupivacaine in a 1:1 ratio with varying block size (4-8) using Stata 15.1 (College Station, TX) ralloc.ado package. When the subject arrives in the operating room, the surgeon/study doctor will contact the pharmacy who will determine treatment assignment and prepare the medication as outlined in Sections 8.3-8.4.

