5.2 Secondary Efficacy Endpoints

- Cumulative Daily In-Hospital Pain Score: 0 (no pain) – 10 (most pain)

Pain Scores are a measure of the subject's postoperative pain that are recorded every four hours by the nursing staff. They are limited by the subject's perception of pain, concomitant pain medication use, and correlation with an abstract scaling system.

- Mean Time to First Opioid Use (hours)

Time to first opioid use is a surrogate marker of postoperative pain. It is limited by variations in anesthesiologist intraoperative analgesia techniques.

- Mean Time to Ambulation (hours)

Time to ambulation is a downstream marker of postoperative pain control. Ambulation is limited by subject motivation and/or physical disability.

- Pulmonary Complications: Pneumonia and Atelectasis requiring Bronchoscopy (y/n)

Pulmonary complications are a downstream marker of postoperative pain control as subjects with chest wall postoperative pain commonly splint with respiration. Splinting is associated with atelectasis and pneumonia.

- Liposomal Bupivacaine and Stand Bupivacaine Adverse Events (y/n):

- Gastrointestinal- nausea, emesis, constipation
- Hypersensitivity- pruritis, urticaria, anaphylaxis
- Cardiac- atrioventricular heart block, cardiac arrest

- Neurologic- dizziness, altered mental status, seizure
- Miscellaneous

To assess if there are differences in the complications between the study groups.

- Length of Stay (days)

Length of stay in the hospital can be used as downstream marker of overall postoperative course. It is limited by attending practice patterns.

- Total Opioid Prescription at Discharge (morphine equivalents in mg)

To assess if there are differences in the amount of opioid prescribed at discharge.

- Total Opioid Use as Outpatient (morphine equivalents in mg)

To assess if there are differences in the amount of opioid used after discharge.

- Direct Costs of Hospital Encounter (dollars)

The interventions in the study add costs over standard of care. It is important to evaluate the burden on the health care system in addition to subject outcomes.

- Quality of Life: Short-Form-8 Health Survey (Rand Health)

A change in quality of life before and after surgery will be assessed. This survey is limited by subject adherence to completion.

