15.3 Analysis of Primary Endpoint

Null Hypothesis: There is no difference in cumulative in-hospital use of opioids in subjects who receive intercostal nerve block and wound infiltration Liposomal Bupivacaine or Standard Bupivacaine during minimally invasive lung resection.

Student's t-test will be used to assess the means of the cumulative total of in-hospital oral morphine equivalents. It is presumed that the data will be normally distributed. If this assumption is not met, transformation or nonparametric tests (Mann-Whitney U test) will be used. Moreover, as there are only 40 subjects per group, it is possible that we do not achieve effective randomization. If this occurs, we will utilize linear regression adjusting for age, sex, race, comorbidity, diagnosis, and procedure performed. A power of 0.8 and 2-sided alpha error set at 0.05 will be used to assess for statistical significance.

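### Surgeon is known before randomisation but appears in neither the allocation nor the analysis; adding it as a fixed factor is a cheap gain in precision, not a repair of bias

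*Combined protocol and SAP*

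**What the plan says.** **Allocation.** Section 8.1 randomises "in a 1:1 ratio with varying block size (4-8) using Stata 15.1". Section 15.6 restates it: "80 Subjects will be randomized to 1:1 to Liposomal Bupivacaine or Standard Bupivacaine by varying block size (4-8". Neither section mentions a stratification factor.

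**Surgeons.** Inclusion criterion 2 in 6.2 reads "Surgeons: [name] MD, [name] MD, or [name] MD". Section 8.1 has the surgeon or study doctor call the pharmacy for the assignment once the subject is in the operating room, so the operating surgeon is fixed by then. Section 8.6 says "the treatment is given in a single episode by the investigators at the conclusion of surgery".

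**Analysis.** The primary test in 15.3 is an unadjusted Student's t-test, with transformation or Mann-Whitney if normality fails. If randomisation is judged not to have been effective (no criterion is given), "we will utilize linear regression adjusting for age, sex, race, comorbidity, diagnosis, and procedure performed". Surgeon is not on that list.

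**Operator variation.** Of length of stay, a secondary endpoint, 5.2 says "It is limited by attending practice patterns". For technique, 8.6 promises that "A standardized approach will be" used by all investigators. For postoperative analgesia it says "a standardized electronic orderset will be utilized". Section 7.1 leaves opioid escalation to the inpatient surgery team.

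**The concern.** Surgeon divides the whole trial into three groups, is recorded at no cost, and may plausibly relate to the outcomes through technique, case mix or discharge habit. Any such variation now goes into the error term. If one surgeon's patients fall more heavily in one arm by chance, neither the t-test nor the contingent regression can account for it, because the regression list covers age, sex, race, comorbidity, diagnosis and procedure only.

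At stake is some power in a trial of 40 per arm, and an awkward reading of the result if the arms turn out visibly unequal in surgeon.

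**Working it through.** **Inputs from the documents (15.6):** mean 35 mg, SD 12 mg, a 19% reduction, 80 subjects, two-sided alpha 0.05. The difference is 0.19 × 35 = 6.65 mg per day.

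**Inputs assumed:** each surgeon's share of cases, and the share of outcome variance due to surgeon (R²). The documents give neither.

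**1. The plan's own power.** Standard error = 12 × √(2/40) = 2.683 mg. Power ≈ Φ(6.65/2.683 − 1.960) = Φ(0.518) = 69.8%; the exact t-test gives 68.7%. The stated 80% is not reproduced: it would need 52 per arm, 104 in total. That is a separate matter and serves here only as the baseline.

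**2. Chance imbalance.** Simulated unstratified blocks of 4, 6 and 8, N = 80:

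| Assumed caseload | Measure | Result |
|---|---|---|
| 40/35/25% | largest surgeon's share, median gap between arms | 7.5 points |
| 40/35/25% | same, gap of 15 points or more | about 20% of trials |
| 40/35/25% | same, gap of 20 points or more | about 8% of trials |
| 33/33/33% and 50/30/20% | any surgeon, gap of 10 points or more | 62–67% of trials |
| 33/33/33% and 50/30/20% | any surgeon, gap of 20 points or more | 14–17% of trials |

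With blocks stratified by surgeon, the last two rows (33/33/33% and 50/30/20%) were 0%.

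**3. What a gap means in mg.** Put all surgeon variance between the largest surgeon (40% of cases) and the other two. Their mean difference is then 12 × √R² / √(0.4 × 0.6).
- R² = 5%: 2.683/0.490 = 5.48 mg. A 7.5-point gap moves the estimate by 0.4 mg and a 15-point gap by 0.8 mg.
- R² = 10%: 3.795/0.490 = 7.75 mg. The shifts are 0.6 and 1.2 mg.

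Both are well inside the standard error of 2.7 mg.

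**4. Power after removing surgeon variance.** Residual SD = 12 × √(1 − R²), surgeon balanced between arms:

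| R² | Residual SD (mg) | Power, normal approximation | Power, exact t |
|---|---|---|---|
| 0 | 12.0 | 69.8% | 68.7% |
| 2% | 11.9 | 70.7% | 69.6% |
| 5% | 11.7 | 72.0% | 70.9% |
| 10% | 11.4 | 74.3% | 73.2% |
| 20% | 10.7 | 79.1% | 78.1% |

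The gain is about 1 point at R² = 2% and 9 points at 20%.

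**5. Adjustment alone, list left unstratified.** Simulated power rose by about 1 point at R² = 5% (67.9 to 68.7%, and 69.7 to 71.0%, for the two caseloads), 3 points at 10% (68.8 to 72.0%, and 68.5 to 71.4%) and 8 points at 20% (68.7 to 76.9%, and 69.1 to 77.1%). If surgeon has no effect, the two degrees of freedom alone cost almost nothing (exact power 68.71% on 78 df, 68.69% on 76 df). Chance imbalance adds a little: in 20,000 simulated trials with caseload 40/35/25% and no surgeon effect, power was 68.8% unadjusted and 67.5% adjusted.

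**6. Type I error.** The planned test (unstratified, unadjusted) gave 0.046–0.051. Stratifying the list but keeping the unadjusted t-test gave 0.041–0.044 at R² = 5%, 0.037–0.038 at 10% and 0.028–0.030 at 20%, which is conservative. With stratification and adjustment it was 0.046–0.050.

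**The case against.** The strongest reply is that unstratified permuted blocks are an accepted design for a blinded single-centre trial of 80 subjects, and that this plan already works to suppress operator variation. Technique is standardised (8.6), with volume, spaces, needle and timing fixed in 8.4.3. All subjects start on the same inpatient and discharge regimens (7, 7.1). Section 6.2 expects no difference between robotic and video-assisted surgery. All of that stands, and it argues for the lower end of the R² range. It does not reach discharge timing, which bears on length of stay, cost and the cumulative in-hospital total tested in 15.3.

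Four stronger readings are tempting, and the documents do not support them.
- A reader might infer that the plan admits attending practice drives outcomes in general. It says so only of length of stay; for time to first opioid and time to ambulation, 5.2 names other limits.
- A reader might take it as stated that each surgeon gives the block personally. Section 8.6 says the investigators do; that these are the three surgeons is a reasonable inference.
- A reader might tie opioid escalation to the attending. Section 7.1 gives it to the inpatient team.
- A reader might think chance imbalance invalidates the test. It does not: the test's alpha already allows for it.

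Stratifying also carries a trade-off. The two preparations look different and masking rests on syringe over-wraps (8.2). If that fails, surgeon-specific sequences are easier to guess than one shared list.

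**Conclusion.** The point holds as one of precision and chance balance. Surgeon is a known three-level factor that the plan neither balances nor adjusts for, and the contingent regression could not correct an imbalance in it. The treatment estimate is unbiased and type I error stays near 5%.

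The size depends on two assumptions that the documents cannot settle. Under a 40/35/25% caseload, a gap of 15 points or more in the largest surgeon's share arises in about one trial in five. The power forgone is roughly 1 to 9 points for R² of 2% to 20% with surgeon balanced. With adjustment alone it is about 1 to 8 points for R² of 5% to 20%, and there is no gain to speak of if surgeon explains only a percent or two. On the plan's 6.65 mg difference, none of these gains brings power to 80%. This is a worthwhile low-cost improvement, not a defect that threatens the conclusion.

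**What to change.** **Section 15.3.** Replace the unadjusted t-test with a linear model of the primary endpoint on treatment and surgeon (two indicator terms). Test the treatment coefficient two-sided at 0.05, and apply the model whatever the observed balance. If a transformation is needed, fit the same model on the transformed scale. If the nonparametric fallback is used, replace Mann-Whitney with a surgeon-stratified rank test (van Elteren). If the contingent regression is kept, add surgeon to its list.

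**Section 15.4.** Use the same treatment-plus-surgeon model for the continuous secondary endpoints.

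Section 15 already promises a detailed SAP before the final data are analysed. The change can go there, before unblinding, even if the list is in use.

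**Cost.** Two degrees of freedom, no new data, and at worst about 1 point of power if surgeon has no effect.

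**Optional, only if the list is not yet in use (8.1, 15.6).** Generate it separately for each surgeon with varying blocks and the same 1:1 ratio. Strata would hold about 16 to 40 subjects under the caseloads assumed (20% to 50% of 80). The cost is up to three incomplete final blocks instead of one, and the predictability trade-off noted above. If this is done, surgeon must be in the model, because the unadjusted t-test is then conservative.
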